8. SUBJECT SAFETY AND ADVERSE EVENTS

Subject safety from pre-procedure evaluation through discharge is the responsibility of the treating physician. The procedural aspects should follow published guidelines for appropriate use criteria. Post-discharge follow-up visits are part of routine standard of care.

All devices used in this study are FDA-cleared and will be used according to current instructions for use (IFU). A device has failed or malfunctioned if it is used in accordance with the IFU but does not perform according to the IFU. Because all devices used in this study are marketed and being used from hospital supply, any device failures or malfunctions will be reported to the device manufacturer per local policy.

In addition, the inability to position the NAVVUS RxI microcatheter at the desired location (~1-2 cm beyond the target lesion) will be considered an event of interest. This device failure rate will be recorded in the eCRF but will not be mandated for reporting to the device manufacturer, as it is not considered a serious adverse event.

8.1 Device Failures, Device Malfunctions, and User Error

In the case of a device failure or malfunction related to the investigation that does not constitute a UADE, the manufacturer should be notified and the device returned to the manufacturing company, if possible. Since these are approved devices, device failures, malfunctions, and user errors will be reported to the appropriate company and FDA per local site policy.

Contact ACIST Medical Customer Service to arrange for a return of the involved hardware and to report the device failure or malfunction.

ACIST Customer Support

[contact]

[contact]

Email: [contact]

9. STATISTICAL ANALYSIS AND DETERMINATION OF SAMPLE SIZE

9.1 Intent-to-Treat Population

The intent-to-treat (ITT) population is consented patients that meet the clinical inclusion/exclusion criteria will be screened in the catheterization laboratory to determine whether they meet the angiographic inclusion/exclusion criteria. Those that meet the angiographic inclusion/exclusion criteria will be officially enrolled in the study and considered part of the intent-to-treat population.

9.2 Per-Protocol Evaluable Population

The per-protocol population is patients in the ITT population that have successfully completed both FFR methods on at least 1 target lesion.

9.3 Primary Endpoint Analysis

9.3.1 Quantitative Method Comparison Between Contrast Fractional Flow Reserves and Adenosine Fractional Flow Reserves

Contrast FFR and aFFR will be quantitatively compared using the procedure described in *CLSI EP09-A3 Measurement Procedure Comparison And Bias Estimate Using Patient Samples Approved Guideline* (18). A summary of this comparison is described below.

The measurements from the 2 methods will be plotted against each other. The aFFR will be plotted on the x-axis, and the cFFR will be plotted on the y-axis. The plot will be examined for highly influential points and heterogeneity of variance along the range of measurement values. In addition, several types of difference plots similar to the Bland-Altman plot will be used to examine whether:

- the size of the variance changes with changing measurement value
- the bias changes with changing measurement value
- the coefficient of variation changes with changing measurement value

Based on the above information, the appropriate model will be applied to describe the relationship of aFFR measured values to their corresponding cFFR values. Assuming:

- sample size of 208 pairs (see the next section) of FFR measurements
- linear model will be applied in quantitative method comparison
- width of the 2-sided 95% CI for the slope is expected to be ± 0.06
- width of the 2-sided 95% CI for the bias is expected to be within ± 0.06

9.3.2 Qualitative Method Comparison Between Contrast Fractional Flow Reserves and Adenosine Fractional Flow Reserves

The qualitative method comparison consists assessing the agreement as to which lesion is flow limiting. If a lesion has an adenosine FFR measurement \leq the cutoff value of 0.8, then the lesion is considered flow limiting. Using the model developed above, the contrast FFR measurement that corresponds to adenosine FFR measurement value of 0.8 will be used as the cutoff value for determining whether a lesion is flow limiting for contrast FFR. The expected cutoff value for the contrast FFR is 0.83.

The 2 methods will be compared qualitatively using the AUC under the ROC curve. The analysis will incorporate the following:

1. The contrast FFR will be the new diagnostic compared to the adenosine FFR as the reference standard.

2. The hypotheses will be designed to demonstrate that that AUC for these two methods is greater than 0.8.

The null and alternative hypotheses are as follows:

[figure not shown]
$$H_0: \text{ROC AUC} \leq 0.8$$

$$H_A: \text{ROC AUC} > 0.8$$

Two hundred and eight pairs of measurements are needed assuming an AUC of 0.9, the ratio of negatives to positives is 1.06, the ratio of the standard deviation of the negatives to the SD of the positives is 1, a 2-sided alpha of 0.05 and a power of 0.9. Figure 2 shows how the sample size changes with varying assumptions of AUC and ratio of negatives to positives.

Figure 2: Sample Size by AUC by various ratio of negative to positive

Contrast FFR compared to Adenosine FFR

The number of pairs of FFR measurements will be tracked and enrollment will be stopped once the requisite number of pairs of FFR measurements have been reached.

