Study Design	The ACCELERATION study is an investigator-initiated, multicenter, prospective, single-arm trial evaluating the method of delivery of contrast for FFR with use of the NAVVUS RXi microcatheter FFR system and the CVi automated contrast injector in patients with intermediate lesion coronary artery disease. Up to 200 subjects undergoing non-emergent PCI from approximately 5 centers will be enrolled. After NAVVUS FFR-guided PCI (with contrast and aFFR measurements), subjects will be contacted for follow-up at 30 days and 1 year by the enrolling site. Primary endpoint results will be reported after all subjects have completed the 30-day clinical follow-up.
Treatment Regimen	Patients with intermediate lesions meeting the clinical and angiographic inclusion/exclusion criteria will be enrolled. NAVVUS FFR will then be performed with contrast and aFFR. Contrast for cFFR will be injected via the ACIST CVi contrast injector with standardized settings, and adenosine for aFFR will be delivered systemically via intravenous infusion. If PCI is performed, a final post-PCI contrast and aFFR will be obtained.
Duration of Subject Study Participation	Sites will see patients for their standard-of-care follow-up visit approximately 30 days after their procedure. Patients will be contacted at 1 year to collect data for the secondary endpoint analysis.
Number of Patients	Up to 200 subjects
Number of Sites	Approximately 5 centers are planned in the US.

Objective/Endpoints for Evaluating the ACIST NAVVUS FFR microcatheter and ACIST contrast power injector.	
Primary Objective/Endpoint:
 
(1) Perform a methods comparison between cFFR and the reference standard aFFR, where cFFR is performed using an automated injector with a standardized volume and rate of delivery of contrast with known osmolality.
 
Secondary Objective/Endpoint:
 
(1) Evaluate the association between final post-PCI FFR and long-term clinical outcomes. The long-term clinical outcomes will include TVR and composite major adverse cardiac events (death, MI, and TVR) at index hospitalization (prior to discharge), 30 days and 1 year.

Statistical Analysis Sample Size/ Power Considerations	Up to 200 patients with intermediate lesions (see statistical analysis plan in protocol for details)

TABLE OF CONTENTS

Statement of Compliance	2
Site Principal Investigator Statement	3
Study Principal Investigator Signature.....	4
Protocol Version and Amendment Tracking	5

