3. STUDY DESIGN

3.1 Overview of Study

The ACCELERATION study is an investigator-initiated, multicenter, prospective, single-arm trial evaluating optimal acquisition techniques of FFR using the NAVVUS RXi microcatheter FFR system in patients with intermediate lesion CAD. The study will determine the accuracy and correlation of cFFR (using the ACIST CVi automated contrast injector) to the current gold-standard aFFR, and evaluate the association of post-PCI FFR to long-term clinical outcomes including TVR and MACE with 1-year follow-up.

Figure 1 depicts the study flow diagram with clinical and angiographic screening criteria. The enrollment cap is controlled at 200 subjects between 5 centers.

Figure 1. Study Design and Treatment Schema

aFFR, adenosine fractional flow reserve; CHF, congestive heart failure; COPD, chronic obstructive pulmonary disease; CVi, ACIST automated contrast injector; dPR, diastolic pressure ratio; FFR, fractional flow reserve; NSTEMI, non-ST-elevation myocardial infarction; PCI, percutaneous coronary intervention; SA, stable angina; UA, unstable angina

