3.2 Procedural Steps

3.2.1 Angiographic Confirmation Eligibility

Patients will be enrolled in the study following angiographic confirmation of a target vessel with an intermediate coronary lesion(s) that meet the inclusion and exclusion criteria. Serial stenosis or diffuse disease can be included if the operator would normally assess these lesions with FFR and plan for PCI if positive. 1 vessel per patient can be enrolled in the study.

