4. SELECTION AND WITHDRAW OF PATIENTS

Up to 200 patients \geq 18 years of age who are eligible for non-emergent PCI will be enrolled.

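### The primary analysis and the stopping rule rest on 208 pairs, but 200 subjects with one vessel each yield at most 200 pre-PCI pairs at one per patient, and the plan does not say which extra pairs count

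*Combined protocol and SAP*

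**What the plan says.** **Pairs.** Section 9.3.2 sizes the AUC test: "Two hundred and eight pairs of measurements are needed assuming an AUC of 0.9", with a null AUC of 0.8, a negative-to-positive ratio of 1.06, an SD ratio of 1, two-sided alpha of 0.05 and power of 0.9. Section 9.3.1 takes its expected interval widths for slope and bias from a "sample size of 208 pairs (see the next section) of FFR measurements". Section 9.3.2 closes with the stopping rule: "enrollment will be stopped once the requisite number of pairs of FFR measurements have been reached".

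**Subjects.** Section 3.1: "The enrollment cap is controlled at 200 subjects between 5 centers". The Synopsis agrees: "Up to 200 subjects undergoing non-emergent PCI from approximately 5 centers will be enrolled". Section 4 repeats "Up to 200 patients".

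**Unit.** Section 3.2.1: "1 vessel per patient can be enrolled in the study". The same section admits several lesions in that vessel: "Serial stenosis or diffuse disease can be included if the operator would normally assess these lesions with FFR". Section 9.2 defines the per-protocol set by completion of both methods on one or more target lesions, and Section 9.3.2 classifies lesions, not patients. Section 3.2.2 requires cFFR and aFFR at each assessment, again after PCI, and again after significant drift. No section says which of these readings make up the pairs to be counted.

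**The concern.** The required number of pairs exceeds the largest number of subjects. At one pre-PCI pair per patient, the stated size cannot be delivered and the stopping rule can never act before the cap does. Losses add to the gap: Section 8 foresees failure to position the microcatheter and Section 12.2 foresees core-lab exclusion of tracings, and no allowance for either is stated.

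If more than one pair per patient is counted, 208 is reachable, but a second gap opens. Pairs from the same patient are expected to be correlated, the sizing formula that reproduces 208 treats them as independent, and the analysis described in Section 9.3 does not mention clustering.

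At stake are the accuracy of the stated power and a stopping rule whose counting unit has to be inferred.

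**Working it through.** **Inputs.** From Section 9.3.2: AUC 0.8 (null) and 0.9 (alternative), R = 1.06 negatives per positive, SD ratio 1, two-sided alpha 0.05, power 0.9. From Sections 3.1 and 3.2.1: 200 subjects, 1 vessel each. Assumed: 0 to 10% of tracings unusable; the documents give no rate.

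**1. Reproduce 208.** The plan names no formula. The standard binormal (Obuchowski) approximation for a one-sample AUC test is

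V(AUC) = 0.0099 × exp(−A²/2) × [(5A² + 8) + (A² + 8)/R], with A = 1.414 × z(AUC).

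- AUC 0.8: A = 1.190, V = 0.1169, square root 0.3419.
- AUC 0.9: A = 1.812, V = 0.0672, square root 0.2592.
- Positives needed = (1.96 × 0.3419 + 1.2816 × 0.2592)² / 0.1² = 100.5, so 101.
- Negatives = 1.06 × 101 = 107.06, so 107.
- Total = 101 + 107 = 208 (209 if the negatives are rounded up).

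The plan's figure is therefore consistent with its own inputs. The Hanley-McNeil variance with the same inputs gives 167, so it is unlikely to be the formula used.

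**2. Pairs available at one per patient.** 200 subjects × 1 vessel × 1 pre-PCI pair = 200, which is 8 short of 208 (8/208 = 3.8%). With 5% or 10% unusable, 190 or 180 remain.

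**3. Power at the deliverable size.** Power = Φ{[0.1 − 1.96 × √(V(0.8)/n)] / √(V(0.9)/n)}, where n = N/2.06 positives.

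| Pairs N | Binormal formula that reproduces 208 | Hanley-McNeil |
|---|---|---|
| 208 | 0.902 | 0.960 |
| 200 | 0.888 | 0.952 |
| 190 | 0.869 | 0.940 |
| 180 | 0.846 | 0.925 |

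The 8-pair shortfall costs 0.902 − 0.888 = 0.014 of power.

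**4. The serial-lesion route to 208.** With no losses, 208 pairs from 200 patients needs 8 patients (4%) to give a second pair: 192 × 1 + 8 × 2 = 208. In the worst case, with the two pairs from a patient perfectly correlated, the effective number is 208² / (192 × 1² + 8 × 2²) = 43,264 / 224 = 193, and power is about 0.875 by the formula in step 1.

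**The case against.** The best defence is that 208 and 200 count different things. Section 9.3.2 speaks of lesions, Section 9.2 allows more than one target lesion, and Section 3.2.1 admits serial stenoses, so 208 lesion pairs from 200 patients is not an arithmetic contradiction. Only 8 patients need a second lesion, and step 4 shows that clustering would then matter little. This softens the point but does not remove it. The plan never states that second-lesion pairs count, and, as described, neither the sizing nor the analysis allows for them. Two limits apply: Section 9.3.1 is a summary of a cited guideline procedure, and Figure 2 cannot be seen in the text reviewed, so the absence of a clustering method can be asserted only for what is written.

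It is also fair to say that repeats after drift most naturally replace a failed reading, since significant drift is itself a ground for exclusion in Section 12.2. They are not a credible way to reach 208.

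A reader might infer something stronger: that post-PCI pairs count, so enrollment could stop far below 200. The share positive at a ratio of 1.06 is 1/2.06 = 0.485; if all of these had PCI and a second pair, 208/1.485 gives about 140 patients. The documents do not support this as the intended reading. Sections 3.2.3, 3.3.2 and 9.4.1 assign post-PCI values to the outcome analysis. And if every post-PCI value were negative, each patient would supply one negative overall, so the ratio would be 1/p for a baseline positive share p; a ratio of 1.06 would need p = 0.943. The scenario shows only why the exclusion of post-PCI pairs should be written down.

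A reader might also infer that the interval widths in Section 9.3.1 are missed. Scaling by √(208/200) moves 0.06 only to 0.061, and the plan presents the bias width as an upper limit, so no missed target is shown.

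**Conclusion.** The point stands as a minor one. At one pre-PCI pair per patient, the 200-subject cap cannot deliver the 208 pairs on which both primary comparisons and the stopping rule rest. If more pairs per patient are meant, the plan does not say which, and its described analysis does not allow for the correlation.

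The practical loss is small: power of about 0.89 at 200 against 0.90 at 208, and 0.85 at 180. This rests on an inferred formula and, for 180, on an assumed 10% of unusable tracings. By Hanley-McNeil, power stays above 0.90 throughout that range. It would be wrong to conclude that 208 was miscalculated, since it follows from the stated inputs, or that the trial is materially underpowered.

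**What to change.** (a) In Sections 9.3.1 and 9.3.2, state that the primary-analysis pair is a pre-PCI cFFR/aFFR pair, and that post-PCI pairs and repeats after drift do not add to the count.

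(b) If one pair per patient is used, restate the deliverable size in both sections as at most 200 pairs, with power of about 0.89 and less if tracings are unusable. Reword the stopping rule so that enrollment stops at the 200-subject cap. Leaving 208 as the trigger would give a rule that can never act.

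(c) If more than one lesion per patient is counted, keep 208, state that enrollment stops at 208 evaluable pre-PCI pairs or 200 subjects, whichever comes first, and use patient-clustered variance for the AUC and the regression.

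The cost is wording, a slightly less favourable stated power under (b), and minor analysis work under (c). Neither the enrollment cap nor data collection changes.

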9.4 Secondary Endpoint Analysis

9.4.1 Assessment of the Relationship Between Post-Percutaneous Coronary Intervention Fractional Flow Reserves and Long-Term Clinical Outcomes

A logistic model will be developed that assesses whether there is a relationship between final PCI FFR (resting, dPR, cFFR, aFFR) and long-term outcomes (death, MI, TVR). The model will include the known covariates for predicting revascularization outcomes: stent length, vessel diameter, diabetes, history of cardiovascular disease, and multi-vessel disease.

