An emerging adenosine-free alternative is contrast-induced FFR (cFFR). Conventional non-ionic radiographic contrast medium has been shown to induce submaximal reactive hyperemia and Pd/Pa ratio measured post-contrast injection has been reported to approximate traditional FFR values (8). A prospective study with 80 patients and 104 intermediate lesions found a strong correlation between cFFR and aFFR ($r=0.94$, $p<0.001$). Receiver operating characteristics (ROC) curve analysis showed an excellent accuracy of a cFFR cut-off of ≤ 0.83 in predicting an FFR value ≤ 0.80 (area under the curve [AUC] 0.97, 95% CI 0.91-0.99, specificity 96.1, sensitivity 85.7). No cFFR value ≥ 0.88 corresponded to an FFR value ≤ 0.80 . These data suggest that cFFR ≤ 0.83 is significant, ≥ 0.88 is non-significant, and borderline values in between should be further assessed with aFFR for induction of maximal hyperemia (8).

A recent international study of 763 patients sought to compare the diagnostic performance of aFFR with the spectrum of alternative FFR modalities, including Pd/Pa, iFR, and cFFR (9). Pd/Pa and iFR had equivalent performances against FFR ≤ 0.80 with ~80% accuracy. cFFR improved this accuracy to 86%. A significant limitation of this study was the lack of a standardized protocol for the type, volume, and rate of intracoronary contrast injection. These considerations were left to the operator’s discretion, including the use of either manual (manifold) injection or an automated injector system, and the choice of contrast agents with different osmolalities. Standardizing these contrast and injection parameters could further improve the diagnostic accuracy of cFFR (9). This hypothesis forms the basis for the current proposed study.

While pre-PCI FFR is now an established modality, there remains limited data on whether immediate, post-PCI FFR might have an important long-term clinical impact. A recent systematic review and meta-analysis included 59 studies evaluating the relationship between post-PCI FFR and clinical outcomes up to 30 months. In general, higher post-PCI FFR values were associated with reduced rates of repeat interventions

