 - iv. Inject contrast to fill guide catheter and wait for return of baseline hemodynamics.
 - v. Press record on ACIST FFR console and then inject contrast at standard settings above for cFFR. Within the first minute of contrast injection, the nadir cFFR value will be logged.
 - vi. The recorded tracings will be captured and saved for an independent FFR core lab review.
- d. Adenosine FFR (aFFR)
 - i. Return of baseline hemodynamics
 - ii. Intravenous adenosine administered at a rate of 140 µg/kg of body weight per minute x 2 minutes will then be performed and the aFFR value logged.
 - iii. If the aFFR is >0.80, then no PCI is performed and this final FFR value will be logged for correlation to long-term outcomes.
 - iv. If the aFFR is ≤0.80, then PCI according to standard techniques will be performed. Post-PCI, the NAVVUS FFR microcatheter will be used to measure resting Pd/Pa, dPR, contrast FFR, and adenosine FFR in the same manner as above with values recorded.
 - v. The recorded tracings will be captured and saved for an independent FFR core lab review.

5. Drift

- a. Drift check will be performed at least once during each procedure and ideally after each use/measurement of the NAVVUS FFR microcatheter
- b. Clinically significant drift will be defined as $> \pm 0.03$ (12).
- c. The presence of any significant drift (yes/no) will be recorded. If there is clinically significant drift, the FFR measurements will be repeated after repositioning of the guide catheter and re-equalization.

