3.2.3 Documentation

Data including baseline clinical and procedural characteristics with all FFR values (pre- and post-PCI resting, dPR, contrast, and adenosine) will be entered into the electronic case report form (eCRF) and used to analyze the primary and secondary study endpoints. These data will be stored in the IBM Clinical Data platform mirroring the NCDR dataset.

The post-PCI (final) aFFR will be used for correlation to 1-year clinical outcomes of death, MI, and TVR. These clinical endpoints will be recorded during the index hospitalization (prior to discharge), 30-day visit (at the routine follow-up appointment or telephone call if this appointment is missed), and at 1 year by telephone. See post-procedure follow-up section for details on data acquisition and definitions.

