3.3.2 Secondary Endpoints

The secondary endpoint is the association between the final post-PCI aFFR and long-term clinical outcomes. The long-term clinical outcomes will include TVR and composite MACE (death, MI, and TVR) during the index hospitalization, 30 days, and 1 year.

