4.3 Angiographic Inclusion/Exclusion Criteria

After the diagnostic angiography, patients having an intermediate lesion(s) meeting the following angiographic criteria will be enrolled:

Inclusion:

Target vessel with an intermediate lesion of 40-70% stenosis by angiographic assessment (a visual estimation by the operator). Serial lesions, diffuse disease, or ostial lesions ("all-comer" lesions) are acceptable if the operator would normally perform FFR and proceed with PCI (or other revascularization) if positive.

Exclusion:

1. ST-segment elevation myocardial infarction culprit lesion or lesions with any thrombus burden

2. Lesions with severe calcification
3. Lesions in a target vessel supplied by a patent graft

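### Section 9.4.1 requires a six-term logistic model on perhaps 5 to 20 events with no provision for few events, and the protocol conflicts with itself on whether patients without PCI enter

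*Combined protocol and SAP*

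**What the plan says.** Section 9.4.1 has two sentences. The first is: "A logistic model will be developed that assesses whether there is a relationship between final PCI FFR (resting, dPR, cFFR, aFFR) and long-term outcomes". The second requires five covariates: "stent length, vessel diameter, diabetes, history of cardiovascular disease, and multi-vessel disease". The section names no estimator and no analysis population. It gives no rule for sparse events or separation, and it does not say which outcome and time point each model uses. Section 9.4.2 covers additional endpoints descriptively. The imputation in section 9.4.3 concerns the primary endpoint. Neither fills these gaps.

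Other sections bear on who and what enters the model:

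- Section 3.2.3: "The post-PCI (final) aFFR will be used for correlation to 1-year clinical outcomes of death, MI, and TVR".
- Section 3.3.2: "The secondary endpoint is the association between the final post-PCI aFFR and long-term clinical outcomes". The heading of 9.4.1 also refers to post-PCI FFR.
- Section 3.2.2, for patients who are not treated: "If the aFFR is >0.80, then no PCI is performed and this final FFR value will be logged for correlation to long-term outcomes".
- Section 3.3.2, on outcomes: "The long-term clinical outcomes will include TVR and composite MACE (death, MI, and TVR) during the index hospitalization, 30 days, and 1 year". Two outcomes at three time points make six possible models.

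**The concern.** There are two linked problems.

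The first is the population. One procedural step sends the FFR of untreated patients into the outcome analysis, while the endpoint definition and the covariate list fit only treated patients. The two readings differ about twofold in sample size. They also ask different questions, because the final FFR of an unstented patient describes an untreated lesion. If the choice is made after outcomes are known, it is data-dependent.

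The second is the number of events. Six terms are required whatever the event count. An unqualified logistic model would normally be fitted by maximum likelihood. With few events per term, that estimator tends to overstate the association and may give no finite estimate because of separation. The estimate at stake is the FFR association, which is the only named secondary endpoint.

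**Working it through.** **Planning figure.** The plan gives no sample size, event count or power for the secondary model. The treated fraction can be inferred only from section 9.3.2, which assumes a negative-to-positive ratio of R = 1.06 and needs 208 pairs. That figure reproduces with the binormal AUC variance V = 0.0099·exp(−A²/2)·[(5A²+8) + (A²+8)/R], where A = √2·z(AUC), and n_pos = (1.96·√V₀ + 1.2816·√V₁)²/0.1². For AUC 0.8 against 0.9, n_pos = 100.4. Rounding up gives 101 positives and 107 or 108 negatives, so 208 or 209 pairs.

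**PCI patients.** The enrolment cap is 200 (section 3.1), and PCI follows an aFFR of 0.80 or below (section 3.2.2). So 200/(1 + 1.06) = 97.1, about 97 patients. The number would be lower if some positive lesions are treated another way, since section 4.3 accepts certain lesions "if the operator would normally perform FFR and proceed with PCI (or other revascularization) if positive".

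**Events.** Section 1 cites 6-month registry rates of death, MI or TVR from 4.9% (best post-PCI FFR stratum) to 20.3% (FFR below 0.90). It also cites 13.2% in the FFR-guided arm of a multivessel trial. Applying these rates here is an assumption.

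- PCI only: 97 × 0.049 = 4.8 and 97 × 0.203 = 19.7, about 5 to 20 events. With six terms that is 0.8 to 3.3 events per term.
- All 200: 9.8 to 40.6 events, or 1.6 to 6.8 per term.

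**Simulation, PCI only (n = 97), one FFR index plus five covariates.** The FFR log-odds ratio is −0.50 per SD. Two standard-normal covariates have log-odds ratios 0.3 and −0.3. Diabetes (35%), cardiovascular history (40%) and multivessel disease (50%) have 0.4, 0.3 and 0.3. All effects and prevalences are assumed; the documents give none. There were 4,000 trials per cell. Maximum likelihood (ML) and Firth fits were compared in the same non-separated trials.

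| Event rate | ML mean overstatement | ML median | RMSE, ML | RMSE, Firth | Separation |
|---|---|---|---|---|---|
| 5% | 34% | 15% | 1.04 | 0.49 | 33% |
| 10% | 20% | 12% | 0.57 | 0.40 | 4% |
| 13.2% | 18% | 13% | 0.45 | 0.36 | 0.9% |
| 20% | 13% | 9% | 0.36 | 0.30 | 0% |

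From unrounded values, Firth RMSE is 30%, 20% and 15% lower at 10%, 13.2% and 20% events. The ML mean and RMSE at 5% are pulled up by near-separated fits; a run that dropped very large estimates gave 23% and 0.68. Mean Firth estimates were −0.47, −0.49, −0.50 and −0.50 down the table.

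**Sensitivity.** Over assumed log-odds ratios of −0.3 to −0.8 at 10% to 20% events, ML mean overstatement was 9% to 26%, median 5% to 16%, and Firth RMSE 12% to 35% lower. A separately programmed simulation, with odds ratios of 1.5 or 2.0 per SD and null to strong covariate effects, gave a mean of 12% to 25%.

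**Bias in proportion.** At 10% events the bias is 0.20 × 0.50 = 0.10, and 0.10²/0.57² = 3.1% of mean squared error. The share was 3% to 4% at 10% to 20% events. Wald coverage was 94.2% to 97.6%, and rejection under no association was 4.6% to 5.8%. In the separately programmed runs the SD of the log-odds ratio was 0.32 to 0.57 and power was 0.18 to 0.72, so imprecision dominates.

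**Very few events.** At an assumed 2% rate and n = 97 (about 2 events), the chance of no event is 0.98^97 = 14%. ML failed or there were no events in about 80% of trials, and Firth estimates were about 22% to 25% too small. The adjusted model is not usable there under either method.

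**The case against.** The strongest reply is that little is really open. The endpoint is defined repeatedly as post-PCI aFFR, stent length fits only stented patients, and one procedural line disagrees. The bias figures rest wholly on assumed effects, medians are lower than means, and no estimator is named, so ML is an inference. Limiting covariates in advance would give about the same error as Firth. Much of this stands. It is why the population point is a reconciliation and the estimator point an improvement in accuracy. But section 3.2.2 states expressly that untreated patients' values are for outcome correlation, and 9.4.1 neither limits the covariates nor provides for few events.

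Three stronger readings are tempting, and the documents do not support them.

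- A reader might infer from the list in 9.4.1 that all four indices enter one model, and from the cited study that "found a strong correlation between cFFR and aFFR" that the aFFR coefficient would then be uninterpretable. Sections 3.2.3 and 3.3.2 name aFFR, no section plans joint entry, and the cited correlation comes from intermediate lesions, not post-PCI values.
- A reader might infer that the secondary test would be invalid. Coverage and type I error were essentially nominal, and bias is a small part of total error.
- A reader might want a bias range for all 200 patients. The runs at that size gave stent length values to unstented patients, so they do not represent a model that the plan defines.

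**Conclusion.** The concern holds for a secondary endpoint only. The conflict over patients without PCI, and the undefined stent length for them, follow from the text and need no simulation. The few-events point depends on three assumptions: only PCI patients enter (about 97), the cited event rates apply, and the FFR log-odds ratio is near −0.5 per SD. On those, at 10% to 20% events, ML overstates the log-odds ratio by about 13% to 20% on average (median about 9% to 14%), and Firth lowers RMSE by roughly 15% to 30%. Near 5 events, ML fails in about a third of trials. Firth makes better use of few events but does not make the estimate precise. The change is worth making because it is cheap; the primary endpoint is unaffected.

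**What to change.** 1. In 9.4.1, name final post-PCI aFFR as the exposure, as 3.2.3 and 3.3.2 already do. Fit resting Pd/Pa, dPR and cFFR one per model as supportive analyses, not jointly.
2. Reconcile 3.2.2 with 3.2.3, 3.3.2 and 9.4.1 on whether patients without PCI enter. If they do, state how stent length is handled for them.
3. Fit the adjusted model for the 1-year outcomes by Firth penalized logistic regression with profile-likelihood intervals, keeping the five listed covariates. Where events are very few (for example index hospitalization, 30 days, or TVR alone with fewer than about 5 events), report counts and rates with Clopper-Pearson intervals, the method in 9.4.2, in place of the adjusted model. The threshold of 5 is a judgement.

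Cost: analysis wording and standard software, with no new data. Because the analysis plan sits inside the protocol, this is an amendment. Under section 6.2 it needs IRB approval at each site unless it counts as a minor administrative change. The statistical cost is shrinkage toward the null: about 0% to 4% at 10% to 20% events and up to about 8% near 5 events. At about 2 events it exceeds 20%, which is why no adjusted model is fitted there. Limiting covariates in advance is an alternative, but it departs from the list in 9.4.1.
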